Adverse Events	Severity grade of the Event (NCI CTCAE version 4.03)	Dose modifications	Toxicity management
			
– Consider, as necessary, discussing with the Study Physician.
Grade 2 (moderate associated with weakness; pain limiting instrumental activities of daily living [ADLs])	Hold study drug/study regimen dose until resolution to Grade ≤ 1 . - Permanently discontinue study drug/study regimen if it does not resolve to Grade ≤ 1 within 30 days or if there are signs of respiratory insufficiency.	For Grade 2: - Monitor symptoms daily and consider hospitalization. - Obtain Neurology consult, and initiate evaluation. - Consider, as necessary, discussing with the Study Physician. - If clinical course is rapidly progressive (particularly if difficulty breathing and/or trouble swallowing), promptly start IV methylprednisolone 2 to 4 mg/kg/day systemic steroids along with receiving input from Neurology consultant - If clinical course is not rapidly progressive, start systemic steroids (eg, prednisone 1 to 2 mg/kg/day PO or IV equivalent); if no improvement within 3 to 5 days, continue additional work up and start treatment with IV methylprednisolone 2 to 4 mg/kg/day - If after start of IV methylprednisolone at 2 to 4 mg/kg/day there is no improvement within 3 to 5 days, consider start of immunosuppressive therapy such as	

Specific immune-mediated reactions

Adverse Events	Severity grade of the Event (NCI CTCAE version 4.03)	Dose modifications	Toxicity management
			
TNF inhibitors (eg, infliximab at 5 mg/kg every 2 weeks). Caution: It is important to rule out sepsis and refer to infliximab label for general guidance before using infliximab.
 
Once the patient is improving, gradually taper steroids over \geq 28 days and consider prophylactic antibiotics, antifungals, or anti-PJP treatment (refer to current NCCN guidelines for treatment of cancer-related infections [Category 2B recommendation]).^a
Grade 3 or 4	For Grade 3: (pain associated with severe weakness; limiting self-care ADLs)	
Hold study drug/study regimen dose until resolution to Grade \leq 1.
 
Permanently discontinue study drug/study regimen if Grade 3 imAE does not resolve to Grade \leq 1 within 30 days or if there are signs of respiratory insufficiency.
	
For Grade 3 or 4 (severe or life-threatening events):
 
Monitor symptoms closely; recommend hospitalization.Obtain Neurology consult, and complete full evaluation.Consider, as necessary, discussing with the Study Physician.Promptly start IV methylprednisolone 2 to 4 mg/kg/day systemic steroids along with receiving input from Neurology consultant.If after start of IV methylprednisolone at 2 to 4 mg/kg/day there is no improvement within 3 to 5 days, consider start of immunosuppressive therapy such as

Specific immune-mediated reactions

Adverse Events	Severity grade of the Event (NCI CTCAE version 4.03)	Dose modifications	Toxicity management
	For Grade 4:	
- Permanently discontinue study drug/study regimen.	
TNF inhibitors (eg, infliximab at 5 mg/kg every 2 weeks). Caution: It is important to rule out sepsis and refer to infliximab label for general guidance before using infliximab.
 
- Consider whether patient may require IV IG, plasmapheresis.- Once the patient is improving, gradually taper steroids over ≥ 28 days and consider prophylactic antibiotics, antifungals, or anti-PJP treatment (refer to current NCCN guidelines for treatment of cancer-related infections [Category 2B recommendation]).^a

Abbreviations: AChE, acetylcholine esterase; ADL, activities of daily living; AE, adverse event; ALP, alkaline phosphatase test; ALT, alanine aminotransferase; ASTc, aspartate aminotransferase; BNP, B-type natriuretic peptide; BUN, blood urea nitrogen; CT, computed tomography; CTCAE, Common Terminology Criteria for Adverse Events; DM, diabetes mellitus; DILI, drug-induced liver injury; ECG, electrocardiogram; ECHO, echocardiogram; GI, gastrointestinal; HBcAB, hepatitis B core antibody; HBeAg, hepatitis B viral protein; HbsAg, surface antigen of the hepatitis B virus; HBV, hepatitis B virus; HCV, hepatitis C virus; HgA1c, hemoglobin A1c; ILD, interstitial lung disease; imAE, immune-mediated adverse event; IG, immunoglobulin; IV, intravenous; LFT, liver function tests; LLN, lower limit of normal; MRI, magnetic resonance imaging; NCI, National Cancer Institute; NCCN, National Comprehensive Cancer Network; PJP, *Pneumocystis jirovecii* pneumonia (formerly known as *Pneumocystis carinii* pneumonia); PO, By mouth; T3, triiodothyronine; T4, thyroxine; TB, total bilirubin; TNF, tumor necrosis factor; TSH, thyroid-stimulating hormone; ULN, upper limit of normal.

^a ASCO Educational Book 2015 “Managing Immune Checkpoint Blocking Antibody Side Effects” by Michael Postow MD.

^b US Food and Drug Administration Liver Guidance Document 2009 Guidance for Industry: Drug Induced Liver Injury – Premarketing Clinical Evaluation.

Abbreviations:

Infusion-related reactions

**Severity grade of Dose modifications
the event (NCI
CTCAE
version 4.03)**

Toxicity management

Any grade

General guidance

For any grade:

- Manage per institutional standard at the discretion of investigator.
- Monitor patients for signs and symptoms of infusion-related reactions (eg, fever and/or shaking chills, flushing and/or itching, alterations in heart rate and blood pressure, dyspnea or chest discomfort, or skin rashes) and anaphylaxis (eg, generalized urticaria, angioedema, wheezing, hypotension, or tachycardia).

Infusion-related reactions

Severity grade of the event (NCI CTCAE version 4.03)	Dose modifications	Toxicity management
Grade 1 or 2	For Grade 1: The infusion rate of study drug/study regimen may be decreased by 50% or temporarily interrupted until resolution of the event. For Grade 2: The infusion rate of study drug/study regimen may be decreased 50% or temporarily interrupted until resolution of the event. Subsequent infusions may be given at 50% of the initial infusion rate.	For Grade 1 or 2: 
– Acetaminophen and/or antihistamines may be administered per institutional standard at the discretion of the investigator.– Consider premedication per institutional standard prior to subsequent doses.– Steroids should not be used for routine premedication of Grade ≤ 2 infusion reactions.
Grade 3 or 4	For Grade 3 or 4: Permanently discontinue study drug/study regimen.	For Grade 3 or 4: 
– Manage severe infusion-related reactions per institutional standards (eg, IM epinephrine, followed by IV diphenhydramine and ranitidine, and IV glucocorticoid).

Abbreviations: CTCAE, Common Terminology Criteria for Adverse Events; IM, intramuscular; IV, intravenous; NCI, National Cancer Institute.

Non-immune-mediated reactions

Severity grade of the Dose modifications event (NCI CTCAE version 4.03)	Toxicity management
Any grade	Note: Dose modifications are not required for AEs not deemed to be related to study treatment (ie, events due to underlying disease) or for laboratory abnormalities not deemed to be clinically significant. Treat accordingly, as per institutional standard.
Grade 1	No dose modifications. Treat accordingly, as per institutional standard.
Grade 2	Hold study drug/study regimen until resolution to Grade \leq 1 or baseline. Treat accordingly, as per institutional standard.
Grade 3	Hold study drug/study regimen until resolution to Grade \leq 1 or baseline. For AEs that downgrade to \leq Grade 2 within 7 days or resolve to \leq Grade 1 or baseline within 14 days, resume study drug/study regimen administration. Otherwise, discontinue study drug/study regimen. Treat accordingly, as per institutional standard.

Non-immune-mediated reactions

**Severity grade of the Dose modifications
event (NCI CTCAE
version 4.03)**

Grade 4	Toxicity management
Discontinue study drug/study regimen (Note: For Grade 4 labs, decision to discontinue should be based on accompanying clinical signs/symptoms, the investigator's clinical judgment, and consultation with the Sponsor.).	Treat accordingly, as per institutional standard.

Abbreviations: AE, Adverse event; CTCAE, Common Terminology Criteria for Adverse Events; NCI, National Cancer Institute.

Note: As applicable, for early phase studies, the following sentence may be added: "Any event greater than or equal to Grade 2, please discuss with Study Physician."

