For patients who do not tolerate the protocol-specified dosing schedule of mRNA-2416, dose reductions may be permitted in order to allow the patient to continue study therapy. If a patient experiences an AE meeting the criteria for DLT as defined in [Section 8.4.2](#), study therapy should be withheld. Following resolution of the toxicity to grade 1 or to the patient's baseline value, the patient may resume study therapy at 50% of the planned dose.

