10.4 DURVALUMAB DOSE MODIFICATION AND TOXICITY MANAGEMENT GUIDELINES

Dose delays are permitted for durvalumab (please see Appendix E for dose modification and toxicity management guidelines), however dose reductions are not permitted for durvalumab.

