10.5 Dose Omissions and Discontinuation of Study Drug Administration

Study treatment may be interrupted for situations other than treatment-related AEs such as medical and/or surgical events or logistical reasons not related to study treatment. Patients should be placed back on study

treatment within 3 weeks of the scheduled interruption, unless otherwise discussed with the Sponsor. The reason for interruption should be documented in the patient's study record.

Patients who have permanently discontinued study therapy will be scheduled for an End of Treatment visit within 14 days (± 2 days) of the decision to permanently discontinue study therapy and assessments will be performed per the Schedule of Events table ([Section 3](#)). Patients who have permanently discontinued study therapy should not be considered withdrawn from the study. They should return for the 30-day and 90-day safety follow-up visit from last dose and the tumor assessment follow-up visits per the Schedule of Events table. If the patient fails to return for these assessments for unknown reasons, every effort (e.g. telephone, email, letter) should be made to contact them.

The following are reasons for discontinuing study therapy without necessarily requiring withdrawal from the study:

- Patients who have completed 6 cycles of study therapy and have an overall tumor assessment of SD or better
- Patients who have experienced a Grade 4 treatment-related AE at any time during study treatment must discontinue from study treatment
- Patients who, in the opinion of the investigator, have incurred a Grade 3 drug-related DLT that has not recovered to Grade 1 or less within 14 days, or has recurred following restarting study therapy at a modified dose level.
- Patients who, in the opinion of the investigator, have incurred unacceptable toxicity that does not meet the pre-determined criteria for DLT (eg, late-onset, treatment-emergent toxicity after the DLT assessment window, or Grade 2 toxicities that are sufficiently durable or unresponsive to supportive intervention as to render them unacceptable in the opinion of the investigator) which has not recovered to Grade 1 or less within 28 days, or has recurred following restarting study therapy at a modified dose level.
- Patients who experience a Grade 3 hypersensitivity reaction or autoimmune events must discontinue from study treatment
- Patients who no longer have lesions that meet criteria for injection
- Pregnancy
- Physician's decision

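### Appendix E's Grade 3 row for non-immune-mediated reactions gives both a hold and a resume instruction for an event at Grade 2 by day 7, and nothing says which prevails

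*Protocol*

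**What the plan says.** Section 10.4 permits durvalumab dose delays and sends sites to the appendix ("please see Appendix E for dose modification and toxicity management guidelines"). The table for non-immune-mediated reactions in Appendix E covers the study drug and the study regimen.

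Its Grade 3 row contains three instructions in sequence:

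1. A hold. The sentence begins "Hold study drug/study regimen until resolution to Grade" and sets the limit at Grade 1 or below, or baseline.
2. A resume rule with two alternatives. The event is down to Grade 2 or below within 7 days, or to Grade 1 or below (or baseline) within 14 days. The words joining the two are "Grade 2 within 7 days or resolve to".
3. A default. The second alternative and the default read "Grade 1 or baseline within 14 days, resume study drug/study regimen administration. Otherwise, discontinue study drug/study regimen".

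The Grade 2 row directly above opens with the same hold sentence and the same limit. It has no 7-day or 14-day provision.

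Two main-text sections cover the same ground:

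- Section 10.3 lets mRNA-2416 injections continue after a toxicity-related interruption once the event has recovered to at least Grade 1 or baseline. For an event meeting DLT criteria, study therapy is withheld and may restart "Following resolution of the toxicity to grade 1" or to the patient's baseline.
- Section 10.5 lists, among the reasons for discontinuing study therapy, patients who "have incurred a Grade 3 drug-related DLT that has not recovered to Grade 1 or less within 14 days".

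**The concern.** A site treating a patient whose Grade 3 event has eased to Grade 2 within a week finds both a hold and a resume instruction in one table cell. If it follows the resume sentence literally, the patient can be re-treated with an ongoing Grade 2 toxicity. That would go against the hold sentence, the Grade 2 row and the threshold in Section 10.3. If it follows the hold sentence, the patient waits.

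The protocol plans about 15 sites and treatment is open-label, so different sites could act differently on the same clinical course. The first stake is patient safety. The second is that differing practice would feed into three descriptive SAP outputs: treatment modifications (Section 7.3.4), reasons for discontinuation (Section 5.1) and TEAEs leading to discontinuation (Section 9.1).

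**Working it through.** There is no sample size, power or error rate to reproduce. The check is to run the row as a decision rule.

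**Inputs.** The hold, resume and default sentences of the Grade 3 row; the Grade 2 row; Sections 10.3 and 10.5.

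**Assumptions.** The event is treatment-related and baseline is below Grade 2. Days are counted from onset of the Grade 3 event. The row does not give a starting point, but the conflict does not depend on the choice.

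Three readings are applied to each recovery path:

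- *Hold*: the hold sentence alone.
- *Literal*: the resume and default sentences as written.
- *Combined*: the 7-day and 14-day limits decide who may restart, and the hold decides when.

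| Recovery path | Hold | Literal | Combined |
|---|---|---|---|
| Grade 2 day 5, never Grade 1 | stay on hold | resume day 5 | stay on hold |
| Grade 2 day 5, Grade 1 day 10 | resume day 10 | resume day 5 | resume day 10 |
| Grade 2 day 5, Grade 1 day 15 | resume day 15 | resume day 5 | resume day 15 |
| Grade 2 day 9, Grade 1 day 14 | resume day 14 | resume day 14 | resume day 14 |
| Grade 2 day 9, Grade 1 day 15 | resume day 15 | discontinue | discontinue |
| Grade 3 to day 14, Grade 1 day 15 | resume day 15 | discontinue | discontinue |
| Grade 2 day 9, never Grade 1 | stay on hold | discontinue | discontinue |

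**Rows 1 to 3** show the conflict. Once the event is at Grade 2 by day 7, the resume sentence allows dosing from that day, while the hold sentence and the Grade 2 row do not.

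**Row 4** is consistent under all readings.

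**Rows 5 to 7** are not a true contradiction. The hold sentence has no time limit, and the default sentence supplies one.

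**Against the main text.** Section 10.3 does not support resumption at Grade 2 on day 5 for mRNA-2416, or for study therapy after a DLT-type event. If the event is a Grade 3 drug-related DLT, rows 1 and 3 also meet the Section 10.5 reason to discontinue, because Grade 1 was not reached within 14 days. Under the literal reading, Appendix E would already have allowed resumption on day 5. Under the combined reading, row 1 stays on hold and row 3 resumes on day 15. Neither reading agrees with Section 10.5.

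**When it matters.** In Arm B, mRNA-2416 is given on Days 1 and 15 of Cycle 1 and then on Day 1 only; durvalumab is given every 4 weeks. With 28-day cycles, Cycle 2 Day 1 falls on study Day 29. A Grade 3 event starting on Day 22 and at Grade 2 on Day 29 (29 − 22 = 7 days) meets the conflict on a day when both agents are due. An event back to Grade 1 before the next dose is treated the same way under the hold and resume sentences.

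**The case against.** The best reply is the combined reading: the two limits settle who may restart rather than discontinue, and the hold settles when. Each sentence then does some work, the Grade 2 row is respected, and nobody is re-treated at Grade 2. This is a possible reading, so a reader should not infer that compliance with all the sentences is impossible. But the protocol does not state it, and the instruction attached directly to both limits is to resume. It also leaves an event that settles at Grade 2 by day 7 on hold with no end point in the row, and it does not agree with Section 10.5 where the event is a DLT.

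A second reply is that Section 10.3 already supplies the Grade 1 or baseline threshold for mRNA-2416, and for study therapy after a DLT-type event. That has weight: the open question is mainly durvalumab after events that are not DLTs. Still, the Appendix E row addresses the whole regimen, and nothing says which text governs.

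A reader might also infer that the row ranks patients wrongly, by re-treating one who is still at Grade 2 while stopping for good one who is back at Grade 1 on day 15. The documents do not support that as an error:

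- The day-15 outcome applies only to a patient still above Grade 2 after day 7. One at Grade 2 by day 7 meets the first alternative.
- The row says discontinue, whereas the Grade 3 or 4 infusion-reaction row specifies permanent discontinuation. Reading the row as final is an inference.
- A rule based on speed of recovery separates early from late improvers by construction. Whether that is desirable is a clinical judgement, not an inconsistency.

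**Conclusion.** The inconsistency is real and narrow. For a related Grade 3 non-immune-mediated event at Grade 2 by day 7, with baseline below Grade 2 and a dose due or delayed, Appendix E gives both hold and resume instructions. No passage says which prevails. Sections 10.3 and 10.5 add to the conflict because neither has a route at Grade 2 by day 7.

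It would be too strong to say that every Arm B patient with such an event receives opposite instructions in practice. With durvalumab every 4 weeks and mRNA-2416 at most every two weeks, many events may resolve before the next dose; the documents give no rate. The affected SAP tables are descriptive, and no endpoint definition, sample size or decision rule changes. The case for correction rests on patient safety and consistent site conduct. It does not depend on which threshold is clinically preferable.

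**What to change.** Reconcile the hold and resume sentences of the Grade 3 non-immune-mediated row with each other, with the Grade 2 row and with Sections 10.3 and 10.5. One action should follow for an event that is at Grade 2 by day 7 and has not reached Grade 1 or baseline. The text should say whether that action is the same for mRNA-2416 and durvalumab, and which passage governs when the event is also a DLT. The threshold is for the sponsor's medical team to decide.

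The cost is one row of a protocol appendix, with matching wording or a cross-reference in Sections 10.3 and 10.5 if needed. No data collection, sample size or SAP method changes.

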11.5. SERUM PHARMACOKINETIC PARAMETERS	27
11.6. STATISTICAL ANALYSIS OF PHARMACOKINETIC PARAMETERS	27
12. INTERIM ANALYSIS	28
13. CHANGES IN THE PLANNED ANALYSIS	28
14. REFERENCES.....	28

List of Abbreviations

AE	adverse event
ALT	alanine aminotransferase
AST	aspartate aminotransferase
AUC	area under the concentration-time curve
BLQ	below the level of quantification
BMI	body mass index
BUN	blood urea nitrogen
CI	confidence intervals
C _{max}	maximum observed concentration
COVID-19	coronavirus disease 2019
CR	complete response
CRF	case report form
CT	computer tomography
CTCAE	Common Terminology Criteria for Adverse Events
CV	coefficient of variation
DCR	disease control rate
DLT	dose-limiting toxicity
DOR	duration of response
ECG	electrocardiogram
ECOG	Eastern Cooperative Oncology Group
eCRF	electronic case report form
irCR	immune-related complete response
irPD	immune-related progressive disease
irPR	immune-related partial response
irRC	immune-related Response Criteria
irSD	immune-related stable disease
ITT	Intent-to-treat
LYRIC	lymphoma response to immunomodulatory therapy criteria
MedDRA	Medical Dictionary for Regulatory Activities
MTD	maximum tolerated dose
NCI	National Cancer Institute
NE	not evaluable

ORR	overall response rate
OX40L	OX40 ligand
PD	progressive disease
PD-1	programmed death 1
PD-L1	programmed death ligand 1
PEG	polyethylene glycol
PET	positron emission tomography
PFS	progression-free survival
PK	pharmacokinetic
PR	partial response
PT	preferred term
QIF	quantitative immunofluorescence
RDE	recommended dose for expansion
RECIST	Response Evaluation Criteria in Solid Tumors
SAE	serious adverse event
SAP	statistical analysis plan
SAS	Statistical Analysis System
SD	stable disease
SOC	system organ class
TEAE	treatment-emergent adverse event
WHO	World Health Organization

1. Introduction

The purpose of the statistical analysis plan (SAP), which is based on most recent version of clinical study protocol amendment version 6 dated 10-JUN-2019, and the case report form (CRF) version 14.0 dated 12-MAR-2021, is to describe the analyses and data presentations for the Sponsor's protocol mRNA-2416-P101. This SAP outlines the types of analyses that will address the study objectives, and explains in detail how the data will be handled and analyzed. It contains the definitions of analysis sets and statistical methods for the analysis of safety, efficacy, pharmacokinetics (PK), and pharmacodynamics.

In addition to the information presented in the statistical methods section of the protocol (Section 13) which provides the principal features of planned analyses for this study, this SAP provides appropriate statistical analysis methodologies in details. It also documents modifications or additions (if applicable) to the analysis plan that are not “principal” in nature and result from information that was not available at the time of protocol finalization.

PPD Biostatistics and Programming team, designee of Moderna Biostatistics and Programming department, will perform the statistical analysis of the efficacy, safety, pharmacokinetic, and pharmacodynamics; Statistical Analysis System (SAS) Version 9.4 or higher will be used to generate all statistical outputs (tables, figures, listings, and datasets). The SAP will be finalized and approved prior to the clinical database lock for primary analysis. If the methods in this SAP differ from the methods described in the protocol, the SAP will prevail.

2. Study Objectives

2.1. Primary Objectives

The primary objectives of the study are as follows:

Phase I

- To determine safety and tolerability of escalating intratumoral doses of mRNA-2416 alone and in combination with durvalumab in patients with relapsed/refractory solid tumor malignancies or lymphoma
- To define the maximum tolerated dose (MTD) and recommended dose for expansion (RDE) and schedule for intratumoral injections of mRNA-2416 alone and in combination with durvalumab in patients with relapsed/refractory solid tumor malignancies or lymphoma

Phase II

- To assess objective response rate of mRNA-2416 alone and in combination with durvalumab in ovarian cancer based on Response Evaluation Criteria in Solid Tumors (RECIST) v1.1

